Dimagi Commcare is HIPAA-compliant; no health information will be stored in the Dimagi platform. This is a secure system and will be further protected by login credentials for limited access, to protect confidentiality. Staff will only access Dimagi to register participants for text messages; [name], the data manager ([name]), and Co-Investigator [name] will have access to the SMS data (number of texts received; number responded) via encrypted, password protected files.

DATA AND SAFETY MONITORING PLAN

Lurie Children's ([name], supervised by [name]) will be responsible for computerized survey programming, data capture, management and analysis. All study information will be identified

through the PID on all forms and computerized files. Computer data files will never contain any identifying information and are encrypted prior to transfer between study sites. All SMS-related data will be securely stored by Dimagi per their HIPAA-compliant privacy policy.

Data entered into the Stata databases will not include any identifying information. Only authorized users with a password will be able to open up the computerized survey, and only those with administrative privileges (i.e., login name and password) will be able to access data. The study staff will use a password to gain access to the software in order to administer it to a participant, but they will have no ability to access the saved data. The Data Manager will set up the database, check data quality, and prepare the data for use. In addition, the database, data structure, and data quality will be routinely reviewed by [name]. Data quality will be examined before statistical analyses are conducted, including examination of missing data, assessment of distributional assumptions, and identification of outliers.

All proposed staff have participated in the NIH required trainings for conduct of studies that involve human subjects, and any future study staff will do so upon hiring. Training for all staff includes (but is not limited to) Human Subjects, Informed Consent, Good Clinical Practice, Quality Management, and Confidentiality and Reporting of Adverse Events. If any study staff discovers an untreated condition in a patient (e.g., onset of physical or mental health condition), they will refer participants to appropriate treatment immediately.

Per guidance provided by the Office of Human Subjects Research at the NIH, an adverse event (AE) is any unfavorable and unintended diagnosis, symptom, sign (including an abnormal laboratory finding), syndrome or disease which either occurs during the study, having been absent at baseline, or, if present at baseline, appears to worsen. A serious adverse event (SAE) is defined as untoward medical occurrences that:

1. result in death
2. are life threatening
3. require (or prolong) hospitalization
4. cause persistent or significant disability/incapacity
5. result in congenital anomalies or birth defects or
6. are other conditions, which in the judgment of the investigators represent significant hazards.

Potential AEs that are unanticipated will be brought to the attention of the study PI and reported immediately to the IRB. All study staff will be trained to recognize and report AEs and SAEs. Possible adverse events will immediately (within 24 hours) be reported to the PIs by the study staff who identify the event. The study PIs will report the AEs and SAEs to the IRB in writing as soon as possible, but within 7 calendar days for death or life-threatening events, and within 15 calendar days for all other AEs or SAEs. The IRB will determine whether it is appropriate to stop the study protocol temporarily or will provide suggestions/modifications to the study procedures as necessary. Possible modifications include adding these possible adverse events to the consent form and re-consenting all study participants. The PIs will be responsible for monitoring participant safety on a monthly basis at regularly scheduled research meetings. They will keep a written log of all events and ensure that the IRB is contacted

immediately. They will also keep a log of the outcome of IRB decisions regarding AEs and apprise the research team of any changes that need to occur as a result of IRB decisions.

Protocol violations are any unapproved changes, deviations, or departures from the procedures of the research study that have not been reviewed and approved by the IRB. Major protocol violations are those that may affect participants' rights or safety, or the completeness, accuracy, and reliability of the study data.

Major violations will include any of the following:

1. The violation has harmed, or posed a significant or substantive risk of harm, to the research participant
2. The violation resulted in a change to the participant's clinical or emotional condition or status
3. The violation has damaged the scientific completeness or soundness of the data collected for the study
4. The violation is evidence of willful or knowing misconduct on the part of the investigator(s)
5. The violation involves **serious or continuing noncompliance** with federal, state or local regulations

Minor protocol violations are those that do not impact or harm participants, including:

1. The violation did not harm or pose a significant risk of substantive harm to the research participant
2. The violation did not result in a change to the participant's clinical or emotional condition or status
3. The violation did not damage the completeness, accuracy and reliability of the data collected for the study
4. The violation did not result from willful or knowing misconduct on the part of the investigator(s)

Study staff will be trained to identify and report all protocol violations to the study PI. The Study PI will determine if the violation is major or minor, will report to the IRB, and will follow up with a plan of corrective action in consult with the IRB.

Data Safety and Monitoring Board

There will not be an appointed data safety and monitoring board.

Data sharing

All data from the project will be made available as de-identified datasets to internal and external investigators requesting access. Data will be made available once primary analysis has been completed, to ensure data cleaning, accuracy, and completeness. The de-identification will include ensuring no protected health information or other potentially identifying information is available in the data set. All those who request data sets will be required to sign a confidentiality and data use agreement that will outline agreed upon use and storage of the de-identified data. The CDC will be provided a copy of the de-identified datasets as required at the end of the funding period. Finally, [name] will be responsible for maintaining a log of requests for data sharing and for sending data via encrypted and secure methods.

IMPORTANCE OF KNOWLEDGE TO BE GAINED

YYALH, particularly racial/ethnic minority youth, have the lowest rates of viral suppression among people living with HIV. Effective interventions exist to support adherence and should be scaled up to ensure equitable access. This proposal addresses these gaps and disparities by scaling up TXTXT, a CDC EBI, in the Midwest via a regional hub model with an established AIDS Education and Training Center (AETC), the Midwest AETC (MATEC). By using both a CDC EBI and HRSA AETC, we build on existing infrastructure, to test an implementation approach with potential for nation-wide scale up. We will simultaneously evaluate effectiveness at the regional level, as well as both the implementation process and outcomes and will engage YYALH, health care providers, and other key stakeholders in the implementation evaluation. This proposal is in line with the Ending the HIV Epidemic research agenda, specifically in efforts to reduce the incidence of HIV, advance cross cutting areas of research, and targeting high risk populations. This study combines behavioral and social science, implementation science, and information dissemination towards the ultimate goal of public health impact. Medication adherence is a key driver of viral suppression and this regional TXTXT initiative, with a longer-term objective of national dissemination and focused on patients at most risk of not achieving viral non-suppression will directly address local, regional, and national goals to End the Epidemic by 2030.

DISSEMINATION AND DATA ACCESS AND MANAGEMENT PLAN

Ann & Robert H. Lurie Children's Hospital of Chicago and the investigative team are committed to the open and timely dissemination of research outcomes. The investigative team has an extensive portfolio of publications, including peer-reviewed manuscripts and book chapters, and national and international conference presentations.

If effective, the scale up of TXTXT has the potential to impact viral load and HIV transmission among racial/ethnic minority youth and young adults in the United States. A multi-faceted dissemination and translation plan targeting various stakeholders is proposed. We will disseminate our findings to both clinical, community and academic audiences, via the following strategies:

1. Members of the research team will present the results of the study in a number of different venues targeting different audiences, including conferences such as the annual meeting of the American Public Health Association, at regional meetings such as HIV planning bodies and Departments of Public Health, and at ID week/grand rounds at regional academic institutions/hospitals.
2. We will present at CDC seminars, group site visits, and symposia to share interim findings
3. We plan to publish our results in appropriate high-impact peer reviewed academic journals.
4. We will create a lay summary to publish on our website, disseminate to community partners, and circulate through the AETC network.

In addition, Lurie Children's maintains a website to disseminate relevant information about research studies conducted by Lurie Children's faculty. Summaries of the scientific presentations will be posted on this website on a regular basis, written primarily for a general audience. All final peer-reviewed manuscripts that arise from this proposal will be submitted to the digital archive PubMed Central.

In addition to disseminating project outcomes the study team will also develop an implementation strategy to integrate TXTXT into HIV clinical care. Guided by the Consolidated Framework for Implementation Research (CFIR),^{37,41} we will meet with key staff from participating sites to review the de-identified/aggregated study data and to identify factors that will facilitate or impede the integration of TXTXT and develop recommended procedures that will facilitate uptake and delivery (e.g., training, monitoring, supervision). In collaboration with MATEC, we will create and disseminate a recommended workflow that will facilitate ease of integration into clinics. Finally, we will create templates, tasks lists, and streamlined processes for patients and providers to guide integration of TXTXT into the clinic flow/care plan.

REFERENCES

- 1 Centers for Disease Control and Prevention. Diagnoses of HIV infection in the United States and dependent areas, 2019. (2019).
- 2 Denning, P. & DiNenno, E. in *XVIII international AIDS conference*.
- 3 Maulsby, C. *et al.* HIV among Black men who have sex with men (MSM) in the United States: a review of the literature. *AIDS Behav* **18**, 10-25, doi:10.1007/s10461-013-0476-2 (2014).

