In this study we propose to use implementation science (IS) to scale up and evaluate the TXTXT evidence-based intervention (EBI) as an effective strategy to increase ART adherence and retention in HIV care, ultimately leading to a suppression of viral load among Black/African American, Hispanic/Latino and other racial/ethnic minority youth and young adults living with HIV (YYALH) participating in the intervention. We hypothesize that those who complete the TXTXT intervention will demonstrate a clinically meaningful increase in ART adherence, viral suppression, and sustained retention in care. Additionally, we hypothesize that the implementation of TXTXT will reach $\geq 80\%$ of the intended participants, will be fully adopted by $\geq 80\%$ of clinic partners, and will achieve $\geq 90\%$ ratings of satisfaction and acceptability. We will use mixed methods to complete our study aims: 1) determine the real-world efficacy of a regional scale up of an EBI – TXTXT -among poorly adherent racial/ethnicity minority YYALH, aged 16-35 years, on our primary outcomes: adherence and viral load suppression at 3-month post initiation of the intervention; and secondary outcome: retention in HIV care at 12-months post baseline, and 2) apply the Consolidated Framework for Implementation Research (CFIR) to describe the implementation process and identify barriers and facilitators needed to be addressed; and measure implementation outcomes of the TXTXT intervention using the RE-AIM framework (Reach, Efficacy, Adoption, Implementation, Maintenance). We will conduct a cluster randomized controlled trial to evaluate the intervention effectiveness (i.e., ART adherence, viral load suppression) at 3-months post-initiation of the intervention. Twelve clinic sites with the ability to enroll up to 50 participants at each site (N=600 participants total) will be trained to administer the TXTXT intervention. Sites will be randomized to either start the intervention immediately (i.e., intervention arm) or waitlisted to start at 3 months post baseline (i.e., comparison arm). In the comparison arm, the study will compare pre-post differences in adherence and viral suppression at 6 months post baseline. Last, we will evaluate retention in HIV care and sustained impact of the intervention at 12 months post baseline for all study participants.

RESEARCH TEAM

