The effort to identify individuals with HIV infection, link and keep them engaged in care, support adherence to ART and suppress viral replication is known as the “HIV care continuum”.⁶ This project focuses on adherence to ART, a step in the HIV care continuum that has not been prioritized among youth and young adults to the same degree as earlier steps in the continuum. Correlates of ART adherence among youth include key psychosocial factors, such as co-morbid mental illness, substance use and HIV-related stigma, among

other factors.⁷ Youth and young adults living with HIV (YYALH) are more likely to disengage from care, delay initiation of ART, and have lower rates of virologic suppression compared to adult populations.⁸⁻¹⁶

However, the most frequently cited reason for non-adherence among YLH is simply forgetting. In a study of youth living with HIV, (aged 12-24 years; n=217), 74% reported the reason for missing doses was that they “forgot”.¹⁷ These findings underscore the need for implementation of reminder interventions, including novel and proven effective intervention strategies such as the TXTXT intervention described herein.

The TXTXT intervention¹⁸ will be adapted, pilot-tested, and scaled up in this project (Appendix A-
<https://www.cdc.gov/hiv/pdf/research/interventionresearch/compendium/ma/cdc-hiv-text-messaging-txtxt-good-ma.pdf>). TXTXT uses a two-way daily text reminder and response system designed by [name] and colleagues, to improve ART adherence for 16-29 years old U.S. adolescents and young adults.¹⁸ Both HRSA and the CDC have designated TXTXT as an effective HIV treatment intervention for ART adherence.¹⁹ While the original TXTXT intervention focused exclusively on ART adherence, for the purposes of the proposed study, we will adapt the intervention to deliver SMS text reminders not only for ART adherence, but also to focus on critical aspects of retention in care (e.g., clinic appointment and pharmacy refill reminders) as our primary outcome; viral suppression, is influenced by both. Further, we have expanded the age range up to 35 years to include young adults who often struggle with adherence as they transition into adulthood and face other developmental milestones.

Figure 1. Diagnoses of HIV infection among men who have sex with men by region and race (United States 2019)

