Determine the real-world effectiveness of a regional scale up of an EBI- TXTXT- among poorly adherent racial/ethnic minority YYALH, aged 16-35 years on our primary outcomes: adherence and viral load suppression at 3-month post initiation of the intervention; and secondary outcome: retention in HIV care, at 12-months post baseline.

Aim 2

Apply the Consolidated Framework for Implementation Research (CFIR) to describe the implementation process and identify barriers and facilitators needed to be addressed; and measure implementation outcomes of the TXTXT intervention using the RE-AIM framework (Reach, Efficacy, Adoption, Implementation, Maintenance).

AIM 1: RESEARCH QUESTION AND OBJECTIVES

Aim 1: Determine the real-world effectiveness of a regional scale up of an EBI- TXTXT- among poorly adherent racial/ethnic minority YYALH, aged 16-35 years on our primary outcomes: adherence and viral load suppression at 3 months post initiation of the intervention; and secondary outcome: retention in HIV care at 12 months post baseline.

RESEARCH DESIGN

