The proposed research uses a cluster randomized controlled trial design to evaluate the effectiveness of TXTXT intervention on adherence and viral load suppression at 3 months post intervention initiation. A total of 12 clinic sites in the Midwest will be randomly assigned to either a 3- month observation period (i.e., comparison arm) or a 3-month intervention period (i.e., intervention arm). At the 3-month mark, sites randomized to the intervention arm will continue with the intervention for an additional 3 months, and sites initially assigned to the comparison arm will switch to the intervention for the 3 months. We will assess initial impact of the intervention by comparing the primary outcomes (i.e., ART adherence and viral load suppression) of the intervention arm to the comparison arm at 3-months post initiation of the intervention. This timepoint (3 months post baseline) was selected based on the findings of the randomized control trial used to establish efficacy of TXTXT.¹⁸ The study will also compare pre-post differences in adherence and viral load suppression for participants in the comparison arm at 6 months post baseline. Secondary outcomes of retention in HIV care and sustained impact of the intervention will be evaluated at 12 months post-baseline. At 3 months, 6 months, and 12 months post baseline, electronic medical record (EMR) data from participating clinics will be used to determine viral load and retention in care measures.

METHODS

Audience and Stakeholder Participation

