A total of 12 clinics and up to N=600 YYALH will be enrolled in this study for evaluation purposes. Each clinic will be able to enroll up to 50 participants for a maximum total of 600 participants. We assume a 20% attrition rate, and therefore the sample size available for analysis will be N=480. Sites will be randomized to either a 3-month observation (i.e., comparison arm) or an immediate start intervention arm; at the end of the first 3-month period comparison arm sites will start the intervention for the 3 months and intervention sites will continue the intervention for an additional 3 months (6 months total). Pre-post EMR data, SMS data, and participant satisfaction data will be collected to determine efficacy, durability, maintenance and satisfaction (see expected outcomes). Rapid interim data analysis and interpretation will occur at 3 months. In Year 3, all clinics and participants (in both the initial control arm or intervention arm) will have their medical records abstracted. In addition, de-briefing interviews will be conducted with clinic staff to assess implementation outcomes. Final analysis and sustainability plan will be conducted and elaborated.

This cluster randomized control study is powered to detect 20% difference in ART adherence (>90%) among participants receiving the TXTXT intervention and the control groups. The power is calculated based on 3 levels hierarchical model design (i.e., randomization at the site level, two measures for each participant). The correlations between the participants within the site is assumed to be 0.05 and correlation within a participant is assumed to be 0.2. The proportion of participants with $\geq 90\%$ ART adherence for the control group is assumed to be 25%, 35%, 45% and 55%. The effect size is assumed to be 10%, 20% and 25%. Given Type I error rate is 0.05, using the mixed model approach, the corresponding power is listed below.³⁵ The sample size with 6 sites in each arm and 50 participants from each site would have 80% power to detect 20% difference at 3 month post baseline.

Table 2: Power (6 sites in each arm, 40 participants from each site)

		proportion of participants with $\geq 90\%$ ART adherence (Control)			
Effect Size	25%	35%	45%	55%	
10%	0.30	0.29	0.28	0.29	
20%	0.82	0.80	0.80	0.83	
25%	0.95	0.94	0.94	0.96	

Track Lessons Learned

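### Two primary outcomes have no success rule, testing order or multiplicity adjustment, so family-wise error is uncontrolled; power is stated for adherence only

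*Combined protocol and SAP*

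**What the plan says.** The Protocol Summary and Aim 1 (Study Objectives) list "our primary outcomes: adherence and viral load suppression" at 3 months after the intervention starts. The Aim 1 Research Design says initial impact will be assessed by "comparing the primary outcomes (i.e., ART adherence and viral load suppression) of the intervention arm to the comparison arm" at that time. The background text on adapting TXTXT differs: it refers to a single primary outcome ("as our primary outcome; viral suppression, is influenced by both").

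The Protocol Summary hypothesis is that those who complete the intervention "will demonstrate a clinically meaningful increase in ART adherence, viral suppression, and sustained retention in care".

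The Aim 1 Data Analysis Plan names model families (GLM, mixed models, GEE). It sets no significance level, testing order, success rule or multiplicity adjustment. The only error rate is in the sample size section. That section opens with "This cluster randomized control study is powered to detect 20% difference in ART adherence" and then, for the same calculation, states "Given Type I error rate is 0.05". It gives no control rate, effect size, intra-cluster correlation or power for viral suppression.

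**The concern.** With two primary outcomes and no decision rule, what counts as a positive trial can be decided after the results are known. Significance on either outcome could then be reported as primary success, and the chance of at least one false positive would exceed 5%.

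The two outcomes also differ in kind. Adherence is self-reported on a visual analogue scale, in a trial where participants know whether they receive reminders. Viral suppression is a laboratory measure and, in the Protocol Summary, the ultimate aim. A result positive on one and null on the other is the case that needs a rule, and the plan has none. Viral suppression is the one outcome the background text singles out as primary, and it has no power statement.

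**Working it through.** **Inputs, all from the sample size section:** 6 sites per arm; 40 analysed per site (50 less 20% attrition); 2 measures per participant; within-site correlation 0.05; within-participant correlation 0.2; control adherence 25, 35, 45 and 55%; type I error 0.05. Sidedness is not stated; two-sided reproduces the table.

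**1. Reproduce Table 2.**
- Design effect = 1 + 2 × (40 − 1) × 0.05 + (2 − 1) × 0.2 = 5.1.
- Effective n per arm = 6 × 40 × 2 / 5.1 = 94.1.
- Power = Φ[(Δ − z·SE₀)/SE₁], where SE₀ uses the pooled proportion and SE₁ the separate proportions.
- For 35% against 55%: SE₀ = √(2 × 0.45 × 0.55 / 94.1) = 0.0725 and SE₁ = √((0.35 × 0.65 + 0.55 × 0.45) / 94.1) = 0.0710. Power = Φ[(0.20 − 1.96 × 0.0725)/0.0710] = 0.792.

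| Control rate, 20-point effect | 25% | 35% | 45% | 55% |
|---|---|---|---|---|
| Table 2 | 0.82 | 0.80 | 0.80 | 0.83 |
| Recomputed, alpha 0.05 | 0.826 | 0.792 | 0.792 | 0.826 |
| Recomputed, alpha 0.025 | 0.742 | 0.701 | 0.701 | 0.742 |

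Eleven of the table's 12 cells agree within 2 points. The exception is 10 points at 25% control (0.321 against 0.30). So the stated power spends the full two-sided 0.05 on adherence.

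**2. Either outcome counts, each tested at two-sided 0.05.** Both the rule and the level for viral suppression are assumptions.
- Independent tests: 1 − 0.95² = 0.0975. The Bonferroni bound is 0.05 + 0.05 = 0.10.
- Correlated tests: 1 − P(|Z₁| < 1.96 and |Z₂| < 1.96), bivariate normal. The documents give no correlation between the two tests, so it is assumed over a range.

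| Assumed correlation | 0 | 0.5 | 0.7 | 0.9 |
|---|---|---|---|---|
| Family-wise error | 9.75% | 9.1% | 8.35% | 7.0% |

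**3. Both must succeed.** A false claim needs a false rejection on at least one null outcome, so the error is at most 5%. If viral suppression had the same power as adherence and the tests were independent (both assumed), joint power would be 0.792² = 0.63 to 0.826² = 0.68. Positive correlation raises this, up to the single-outcome 0.79 to 0.83 at perfect correlation.

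**4. Holm.** The smaller p-value is tested at 0.025 and, if it passes, the other at 0.05. Adherence power is therefore at least the alpha-0.025 row above. With equal power and independent tests (assumed), it is:
- 0.701 + (0.792 − 0.701) × 0.701 = 0.765
- 0.742 + (0.826 − 0.742) × 0.742 = 0.804

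**5. Can the second primary outcome be measured at 3 months?** The Research Design and the Retention section both use medical-record viral load at 3 months. The Study participation summary and its timepoint table show only a survey at 3 months, with record pulls at baseline, 6 and 12 months.

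**The case against.** The best defence is that the documents never commit to the rule that inflates the error. No level is attached to viral suppression. The hypothesis joins its outcomes with an and, which points towards requiring both; under that rule, or an ordered test, 5% is kept. The protocol also calls adherence a key driver of viral suppression, so positive correlation is plausible and 9.75% is the extreme.

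Much of this stands, and it rules out three stronger readings that a reader might infer:
- That the plan tests each outcome at 0.05. The figure appears once, for adherence power, so a 0.05 test of viral suppression is an inference.
- That the trial's error rate is known to exceed 5%. This holds only if success on either outcome counts.
- That a false positive on adherence alone occurs at nearly double the stated rate. A 0.05 test of adherence has a 5% false-positive rate. With independent null tests, adherence is significant and viral suppression is not in 0.05 × 0.95 = 4.75% of trials. The 9.75% is the chance of at least one false positive among the two.

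The defence does not remove the gap. The hypothesis is not a decision rule: it also includes retention, which the plan calls secondary. Nothing in the plan prevents success on either outcome from being reported as a positive trial.

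**Conclusion.** The concern holds in this form: the plan leaves family-wise error over its two primary outcomes uncontrolled. Under an either-outcome rule with two tests at 0.05, the error runs from 7.0% to 9.75% over assumed correlations of 0.9 to 0. Under a both-required rule it is at most 5%, but the stated 80% then describes adherence alone, not trial success.

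Viral suppression has no power statement, and Table 2 cannot simply be carried over. Patients may enrol with a viral load of at least 200 copies/mL, with self-reported poor adherence, or with both, so the control rate for suppression may differ from that for adherence. All power figures here use the normal approximation that reproduces Table 2.

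**What to change.** Before analysis:

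1. Reconcile the background text (viral suppression as the single primary outcome) with Aim 1 (two primary outcomes).
2. Prespecify one rule that holds the overall two-sided error at 0.05:
   - **Holm across both outcomes.** Show Table 2 also at the 0.025 first step (0.70 to 0.74 for 20 points), labelled as a lower bound on adherence power. Guaranteeing 80% at 0.025 would need an effective 107 to 117 per arm; multiplied by 5.1 and divided by 80 measures per site, that is 6.8 to 7.5, so 7 to 8 sites per arm.
   - **A fixed sequence.** Adherence first keeps the stated adherence power but still allows a positive result on self-report alone. The sponsor should choose the order with that in view, after step 1.
3. State power for viral suppression over a range of control rates, effect sizes and intra-cluster correlations, labelled as assumptions.
4. Reconcile the Research Design and Retention sections (record-based viral load at 3 months) with the participation schedule (survey only at 3 months), so that it is clear the second primary outcome can be tested then.

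The cost of the testing rule is a few sentences in the SAP. Holm lowers the stated adherence power somewhat; adherence first in a fixed sequence leaves it unchanged. Step 4 may add a record extraction if none is planned at 3 months.
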